#### **5.4.2. Discontinuation of Study Drug**

Permanent discontinuation of study drug will not require the subject to be withdrawn from the study. Subjects should continue where possible to be followed and disease status assessed. Upon permanent discontinuation of subcutaneously-administered blinded sirukumab or matching placebo, corticosteroid dose and treatment will be at the discretion of the investigator.

Study drug (subcutaneously-administered blinded sirukumab or matching placebo) must be permanently discontinued for any of the following:

1. The investigator (in consultation with the medical monitor) believes that for safety reasons (e.g., adverse event) it is in the best interest of the subject to stop treatment.
2. Severe allergic reaction or anaphylactic reaction resulting in bronchospasm with wheezing, or dyspnea requiring ventilatory support, or symptomatic hypotension with a > 40 mmHg decrease in systolic blood pressure that occurs following study drug administration.
3. Reaction suggestive of serum sickness occurring 1-14 days after study drug administration. These may be manifested by symptoms of myalgias, arthralgias, fever, rash, pruritus, facial, hand, or lip edema, dysphagia, urticaria, sore throat, and/or headache.

4. Adverse events (AEs) or laboratory abnormalities indicative of safety concerns which are significant enough to discontinue study drug in the opinion of the investigator.
5. Pregnancy.
6. Liver function abnormalities as specified in Section 5.4.3.
7. Opportunistic infection, ie, an infection by an organism that usually causes disease only in a host whose resistance is lowered (eg, Pneumocystis jirovecii, coccidioidomycosis, Mycobacterium avium).
8. Active or latent TB.
9. Malignancy, excluding nonmelanoma skin cancer.
10. Demyelination, either central or peripheral.
11. Two confirmed consecutive absolute neutrophil counts of  $<0.5 \times 10^9$  cells/L.
12. Two confirmed consecutive platelet counts  $<50 \times 10^9$  cells/L.
13. Acute diverticulitis requiring antibiotic treatment.
14. Gastrointestinal perforation.

Subjects must **not** receive blinded subcutaneous sirukumab or matching placebo during the course of a serious infection. Subjects who temporarily discontinue blinded sirukumab or matching placebo due to an infection or other reasons should continue to follow the prednisone taper schedule.

Discontinuation of blinded subcutaneous sirukumab or matching placebo must be strongly considered for subjects who develop a serious infection such as sepsis or meningoencephalitis, and considered for subjects who have serious infections requiring hospitalization or IV antibiotic therapy.

[figure not shown]
Discontinuation of blinded subcutaneous sirukumab or matching placebo should also be considered for severe injection-site reactions.

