#### **4.2.2. Part B: 104-week extension phase**

All subjects who complete Part A of the study will be eligible to enter part B. The two populations of subjects expected to enter into Part B are:

- Subjects in remission at the primary 52-week endpoint. These subjects will discontinue blinded study drug treatment on entry into Part B and will be followed for maintenance of response. However, in the event of a flare, they will have the option to receive, at the discretion of their Investigator, open-label sirukumab 100 mg SC q2w for a maximum of 52 weeks during the first 52 weeks of Part B.
- Subjects not in remission, at the primary 52-week endpoint or subjects who have not been able to taper prednisone during Part A. Upon entry into Part B, these subjects will have the option to receive, at the discretion of the Investigator, open-label sirukumab 100 mg SC q2w for a maximum of 52 weeks.

For subjects who newly flare at any time during the 1st 52 weeks of Part B and require a treatment change, open-label sirukumab 100 mg SC q2w can be initiated within the first 52 weeks of Part B. The duration of treatment will be at the discretion of the investigator but must not exceed 52 weeks. Treatment with open-label sirukumab 100 mg SC q2w must complete by Week 104 (the end of the extension phase). Corticosteroid use or the initiation of methotrexate therapy alone or in addition to sirukumab treatment during Part B will be at the discretion of the investigator.

Treatment with open-label sirukumab 100 mg SC q2w must complete by Week 104 (the end of the extension phase). Adjustments in corticosteroid dose or the initiation of methotrexate therapy alone or in addition to sirukumab treatment during Part B will be at the discretion of the investigator.

Investigators should carefully consider the individual benefit-risk of continuing sirukumab in those subjects that continue to experience flares or persistent disease activity following the start of open label treatment.

Upon **study** completion, decisions on treatment options for individual subjects will be at the discretion of the investigator.

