#### 4.6.1. Risk Assessment

Potential Risk of Clinical Significance	Summary of Data/Rationale for Risk	Mitigation Strategy
Investigational Product (IP) [sirukumab]		
TB reactivation	Cases of TB reactivation have been reported with IL-6 antagonists, such as tocilizumab and sirukumab.	Inclusion only of subjects with no evidence of active or latent TB infection, negative diagnostic TB test at Screening and Screening chest radiograph showing no evidence of current or previous pulmonary TB (Section 5.1 Bullet 4). Evaluation of TB throughout the study by use of a TB questionnaire and a TB test (Section 7.5.7)
Serious/opportunistic infections	IL-6 deficient mice have been noted to be susceptible to infections with Listeria , monosytogenes , Toxoplasma gondii , and Candida albicans [Dalrymple, 1995; Romani, 1996; Suzuki, 1997]. Serious, life-threatening infections such as septic shock, some of which have been fatal, have occurred in subjects receiving sirukumab.	Exclusion of subjects with an active current or history of recurrent bacterial, viral, fungal, mycobacterial, or other infection or those with a prior episode of major infection (serious infectious event). Monitoring of serious and opportunistic infections by IDMC.
Hypersensitivity	Serious allergic reactions (eg, anaphylaxis) have been reported with the administration of mAbs, including sirukumab, and may occur during or after the administration of the mAbs.	Exclusion of subjects with severe allergic reactions to monoclonal antibodies, human proteins, or excipients. Subjects will be made aware of the potential risk, the signs and symptoms of such reactions, and the importance of immediately seeking medical attention. Discontinuation of blinded subcutaneous study drug in the event of a severe allergic reaction. Monitoring of serious allergic reactions by IDMC; adjudication and classification of these events using Sampson criteria (Sampson, 2006) by

Potential Risk of Clinical Significance	Summary of Data/Rationale for Risk	Mitigation Strategy
		sponsor safety review team will be implemented.

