Gastrointestinal perforation	Upper and lower GI tract perforations occurred in the anti-IL-6 receptor (tocilizumab) & the anti-IL6 (sirukumab) Phase III programs. Sirukumab binds to IL-6 and prevents binding to IL-6 receptor (IL-6R). Tocilizumab binds to IL-6 R to prevent IL-6 signalling. Potential differences in safety between agents that bind to the IL-6 receptor versus ones that bind to the IL-6 ligand (sirukumab) warrants further study.	Exclusion of subjects with a history of diverticulitis, inflammatory bowel disease, or other symptomatic GI tract condition that might predispose to bowel perforation. Investigators should closely monitor for GI perforations with a high degree of suspicion. Monitoring of gastrointestinal perforations by IDMC.
Cytopenias	Neutropenia and thrombocytopenia have occurred in sirukumab studies, including severe thrombocytopenia associated with bleeding. Most patients who developed neutropenia while being treated with sirukumab did not develop infections, and most patients who developed thrombocytopenia did not experience bleeding events. Decreases in platelet counts have also been observed.	Exclusion of subjects with absolute neutrophil count (ANC) $<2 \times 10^9/L$ , platelet count $<140 \times 10^9/L$ , WBC count $<3.5 \times 10^9/L$ , ALC $<0.5 \times 10^9/L$ . Discontinuation of blinded subcutaneous study drug for subjects with 2 confirmed consecutive absolute neutrophil counts of $<0.5 \times 10^9$ cells/L or platelet counts $<50 \times 10^9$ cells/L. Monitoring of cytopenias by IDMC.
Lipid increases	Increases in blood total cholesterol, LDL, HDL, and triglycerides have occurred in sirukumab-treated subjects. No dose response was observed.	Monitor HDL/LDL levels, administer a cholesterol lowering agent if indicated.
Liver enzyme increases	Transient asymptomatic increases (1 to 3 x ULN, sometimes $> 5 \times$ ULN but $< 8 \times$ ULN) in blood ALT and AST values have been observed in subjects in completed and ongoing studies of sirukumab. Six subjects have had ALT or AST $>3 \times$ ULN and bilirubin $>2 \times$ ULN; all 6 had received	Exclusion of subjects with AST or ALT $>2.0 \times$ ULN, or total bilirubin $>ULN$ with the exception of Gilbert's disease. Inclusion of pre-defined liver chemistry discontinuation criteria (Section 5.4.3). Monitoring of hepatic abnormalities by IDMC.

Potential Risk of Clinical Significance	Summary of Data/Rationale for Risk	Mitigation Strategy

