## 6. STUDY TREATMENT

### 6.1. Investigational Product and Other Study Treatment

The term ‘study treatment’ is used throughout the protocol to describe any combination of products received by the subject as per the protocol design. Study treatment may therefore refer to the individual study treatments or the combination of those study treatments. Study treatment specifically related to sirukumab and matching placebo is distinguished by the use of the terminology “subcutaneously-administered blinded study drug or treatment (sirukumab and matching placebo)”.

Sirukumab and matching placebo will be supplied by the Sponsor. Both sirukumab and matching placebo will be administered subcutaneously using an autoinjector device. The sirukumab drug product provided for this study is supplied in a 1 mL Pre-filled Syringe (PFS) fitted with a spring-powered, disposable autoinjector device for single use SC administration of liquid biologic drug products (SmartJect Autoinjector) that is permanently assembled on the syringe. The sirukumab PFS is aseptically filled to deliver a dose of either 100 mg/1.0 mL or 50 mg/1.0 mL of sirukumab in a Becton-Dickinson (BD) Hypak, 1 mL glass SCF (presiliconized) syringe barrel with a 26 gauge (G) ½ inch fixed needle, an elastomeric needle shield, and a fluoropolymer coated elastomeric plunger stopper. Placebo for sirukumab PFS provided for this study is supplied in a matching presentation.

However, as a contingency, sirukumab may also be supplied as a single-use prefilled syringe-Ultrasafe (PFS-U), which is a ready to use liquid filled 1-mL-long syringe product supplied with a passive safety needle guard (UltraSafe Passive Delivery System, Safety Syringes, Inc.) for SC administration. Placebo for sirukumab PFS-U will also be supplied as appropriate.

The needle shield on the PFS (either assembled into UltraSafe needle guard or autoinjector/prefilled pen) is made with a derivative of natural rubber latex, which may cause allergic reactions in individuals sensitive to latex.

Prednisone for the pre-specified standard blinded taper will be provided by the Sponsor. The prednisone used in the blinded taper of this study is manufactured by Jubilant Cadista (Salisbury, MD) and supplied to the Sponsor by Myoderm (Norristown, PA).

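### Section 5.4.2 words its stopping rules for blinded product, so read literally they miss open-label sirukumab in Part B; for four criteria no other text fills the gap

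*Protocol*

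**What the plan says.** Part B offers open-label drug. For subjects who newly flare, "open-label sirukumab 100 mg SC q2w can be initiated within the first 52 weeks of Part B" (Protocol 4.2.2). Subjects not in remission at Week 52, or unable to taper, may start on entry. Treatment may last up to 52 weeks.

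The stopping rules are in Protocol 5.4.2. The lead sentence is "Study drug (subcutaneously-administered blinded sirukumab or matching placebo) must be permanently discontinued for any of the following", followed by 14 numbered criteria. Below the list, subjects must not "receive blinded subcutaneous sirukumab or matching placebo during the course of a serious infection". Two softer clauses follow: "Discontinuation of blinded subcutaneous sirukumab or matching placebo must be strongly considered for subjects who develop a serious infection" and "Discontinuation of blinded subcutaneous sirukumab or matching placebo should also be considered for severe injection-site reactions".

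Two rows of the risk table in Protocol 4.6.1 carry the same restriction: "Discontinuation of blinded subcutaneous study drug in the event of a severe allergic reaction" and, in the cytopenia row, "Discontinuation of blinded subcutaneous study drug for subjects with 2 confirmed consecutive absolute neutrophil counts".

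Protocol 6.1 sets the terminology: "Study treatment specifically related to sirukumab and matching placebo is distinguished by the use of the terminology". The label that it then gives contains the word *blinded* and does not mention open-label drug.

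**The concern.** Open-label sirukumab is by definition not blinded product. On a literal reading, a Part B subject on open-label drug who has a GI perforation meets no mandatory stop, although the same event on blinded product would end dosing.

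The exposure is not trivial. Open-label treatment is at the higher of the two doses. For subjects from Arms D and E it would be their first sirukumab in the study. Protocol 7.5.1.5 names infection as an identified risk, with fatal cases, and Protocol 4.6.1 reports GI perforations in the sirukumab Phase III program. A site should not have to infer whether a mandatory safety rule applies.

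**Working it through.** No power, alpha or event figure is involved. The check is whether each rule in 5.4.2 is stated elsewhere in the current text without the word *blinded*.

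**Step 1: does unqualified *study drug* include open-label sirukumab?** Yes. Table 5 footnote 1 speaks of study drug being started when it means open-label sirukumab. Section 4.1 counts open-label treatment in Part B when it sets the 16-week follow-up after the last dose of study drug. So a rule stated for study drug without qualification reaches Part B.

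**Step 2: the 14 criteria.**

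| Criterion | Rule elsewhere without *blinded* | Reaches open-label drug? |
|---|---|---|
| 1, 4 investigator judgement | 4.2.2 leaves duration to the investigator | Yes, in effect |
| 2 severe allergic reaction | 7.5.1.6 | Yes |
| 3 serum-sickness-type reaction | 7.5.1.6, severe reactions only | At most when severe |
| 5 pregnancy | 7.5.2, Appendix 2 | Yes |
| 6 liver | 5.4.3, Appendix 3 | Yes |
| 7 opportunistic infection | Appendix 7, Germany | Only there, and as a hold |
| 8 TB | 7.5.8 | Active TB yes; latent TB is interrupt-and-treat |
| 9 malignancy | None | No |
| 10 demyelination | None | No |
| 11, 12 neutrophils, platelets | Table 7 | Yes |
| 13 diverticulitis needing antibiotics | None | No |
| 14 GI perforation | None | No |

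Tally: 5 covered (2, 5, 6, 11, 12), 2 by judgement (1, 4), 1 covered for active TB only (8), 1 at most partly covered (3), 1 with a German hold only (7), and 4 with nothing (9, 10, 13, 14). 5 + 2 + 1 + 1 + 1 + 4 = 14. Outside 5.4.2, the last four appear, if at all, as exclusion criteria, reporting duties or monitoring items.

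**Step 3: the serious-infection hold.** Two other sets of rules require open-label drug to be interrupted or stopped for infection. Section 7.5.8 covers TB in every country. Appendix 7 covers serious or severe infection in Germany. Appendix 7 also keeps Dutch subjects out of Part B, so the gap cannot arise there. In the remaining countries, no mandatory rule bars open-label dosing during a serious infection other than TB.

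**Step 4: how many places carry the wording.** Section 5.4.2 has six: the lead sentence, the hold, the sepsis clause, the injection-site clause, and two sentences on corticosteroid dose and the prednisone taper. Section 4.6.1 has two. 6 + 2 = 8. The two prednisone sentences need no change: 8 − 2 = 6. The term in 6.1 makes 7 edits.

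**The case against.** The best reply is that *blinded* is only a label. Section 6.1 introduces it for all study treatment related to sirukumab and placebo, with no limit to Part A. Table 7 sends readers to 5.4.2 for study drug in general. Appendix 9 (Amendment 3, items 18 and 19) shows the infection hold previously said simply study drug, and gives the reason for the terminology as telling the injected product apart from prednisone. A sensible investigator would stop open-label drug after a perforation anyway. Discretion to withdraw for safety (5.4.1), 24-hour reporting of malignancies and perforations (7.5.1.3) and IDMC monitoring (4.6.1) all apply.

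Much of this stands. It makes a drafting slip the likely explanation and limits the practical harm. A reader might infer that the sponsor chose to exempt Part B; nothing in the documents states that intent. But context does not supply the missing rule. The label in 6.1 itself says *blinded*, the protocol uses open-label sirukumab as a distinct term, and no current sentence clearly extends the list to it. Discretion, reporting and monitoring are not mandatory stops.

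A reader might also infer that nothing outside Germany bars open-label dosing during a serious infection. That goes too far, because the TB rules in 7.5.8 apply everywhere. Nor do all 14 criteria fail: the table shows that most are restated or rest on judgement.

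**Conclusion.** The wording is wrong as it stands, most likely by accident, and it concerns patient safety. Read literally, the stop list, the infection hold and the two *consider* clauses do not reach open-label sirukumab. The substantive gap is narrower than that: criteria 9, 10, 13 and 14 in every country with a Part B; criterion 7, with only a hold in Germany; criterion 3 unless the reaction is severe; and the infection hold outside Germany, TB excepted. The sepsis and injection-site clauses are advisory for blinded drug too, so little turns on them.

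This rests on reading *blinded* literally and on unqualified *study drug* including open-label sirukumab, as Table 5 and Section 4.1 indicate. No number of affected subjects can be given. The documents state no rates for these events in this study and do not say how many subjects received open-label drug. SAP 1.1 records termination on 10 October 2017, early withdrawal visits completed by 30 November 2017, and a limited number of subjects completing Week 52. It would be wrong to infer that anyone was dosed after such an event.

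**What to change.** **Text.** Write *subcutaneously-administered sirukumab (blinded or open-label) or matching placebo* in the 5.4.2 lead sentence, infection hold, sepsis paragraph and injection-site paragraph, in the allergy and cytopenia rows of 4.6.1, and in the 6.1 term. Leave the two prednisone sentences in 5.4.2 as they are. The cost is seven wording edits, with no new visits, data or patients.

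**Report.** Start from the outputs on adverse events leading to permanent discontinuation or interruption of SC IP (SAP 9.1.5 and 9.1.6), which SAP Section 11 carries into Part B. These show events after which drug was stopped or held, not events after which it continued. So cross-check the AE and AESI listings (SAP 9.1.1, 9.1.8) against the exposure and last-dose listings (SAP 7.2.1, 5.1), and confirm that these include open-label injections. Demyelination is not an AESI group, so take it from the AE listing. The Part B AESI summaries cannot answer the question. One by-line is ever/never open-label, the other pools SC IP with open-label drug, and action taken is a subject-level worst case.

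**Separate item.** Criterion 8 requires a permanent stop for latent TB, while 7.5.8 allows dosing to resume once treatment has begun. That conflict affects blinded drug equally and should be resolved on its own.

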#### **5.4.3. Liver Chemistry Stopping Criteria**

**Liver chemistry stopping and increased monitoring criteria** have been designed to assure subject safety and evaluate liver event etiology (in alignment with the FDA premarketing clinical liver safety guidance).  
<http://www.fda.gov/downloads/Drugs/GuidanceComplianceRegulatoryInformation/Guidances/UCM174090.pdf>

[figure not shown]
Subjects meeting the liver chemistry stopping and increased monitoring criteria may be required to temporarily or permanently discontinue study treatment.

**Phase III-IV Liver Chemistry Stopping and Increased Monitoring Algorithm**

Liver Safety Required Actions and Follow up Assessments Section can be found in [Appendix 3](#)

**Phase III-IV Liver Chemistry Increased Monitoring Algorithm with Continued Therapy for ALT  $\geq 3xULN$  but < 8xULN**

Liver Safety Required Actions and Follow up Assessments Section can be found in [Appendix 3](#)

#### 5.4.3.1. Study Treatment Restart or Rechallenge

Study treatment restart or rechallenge after liver chemistry stopping criteria are met by any subject participating in this study is not allowed.

#### 5.4.4. QTc Stopping Criteria

An ECG is required only at screening. If an additional ECG is performed during study participation outside of study requirements and any of the bulleted criteria below are met, study treatment should be discontinued and the Medical Monitor should be contacted. There is no requirement for the subject to be withdrawn from the study.

QTc Stopping Criteria:

- QTc  $\geq$  530 msec (all subjects)
- OR
- Change from baseline of QTc  $>$  60 msec.

The *same* QT correction formula *must* be used for *each individual subject* to determine eligibility for and discontinuation from the study. This formula may not be changed or substituted once the subject has been enrolled.

- For example, if a subject is eligible for the protocol based on QTcB, then QTcB must be used for discontinuation of this individual subject as well.
- Once the QT correction formula has been chosen for a subject's eligibility, the *same formula* must continue to be used for that subject *for all QTc data being collected for data analysis*. Safety ECGs and other non-protocol specified ECGs are an exception.
- The QTc should be based on averaged QTc values of triplicate ECGs obtained over a brief (e.g., 5-10 minute) recording period.

### 5.5. Subject and Study Completion

A completed subject is one who has completed both Part A and Part B (and the maximum of a 16-week follow-up upon completion of Part B, if applicable) of the study. As discussed in Section 4.1, the up to 16-week follow-up visit is only for subjects who are withdrawn prematurely from the study or for those subjects in Part B of the study who **complete** open-label treatment with sirukumab 100 mg SC q2w after Week 88.

The end of the study is defined as the last subject's last visit.

## 6. STUDY TREATMENT

### 6.1. Investigational Product and Other Study Treatment

The term ‘study treatment’ is used throughout the protocol to describe any combination of products received by the subject as per the protocol design. Study treatment may therefore refer to the individual study treatments or the combination of those study treatments. Study treatment specifically related to sirukumab and matching placebo is distinguished by the use of the terminology “subcutaneously-administered blinded study drug or treatment (sirukumab and matching placebo)”.

Sirukumab and matching placebo will be supplied by the Sponsor. Both sirukumab and matching placebo will be administered subcutaneously using an autoinjector device. The sirukumab drug product provided for this study is supplied in a 1 mL Pre-filled Syringe (PFS) fitted with a spring-powered, disposable autoinjector device for single use SC administration of liquid biologic drug products (SmartJect Autoinjector) that is permanently assembled on the syringe. The sirukumab PFS is aseptically filled to deliver a dose of either 100 mg/1.0 mL or 50 mg/1.0 mL of sirukumab in a Becton-Dickinson (BD) Hypak, 1 mL glass SCF (presiliconized) syringe barrel with a 26 gauge (G) ½ inch fixed needle, an elastomeric needle shield, and a fluoropolymer coated elastomeric plunger stopper. Placebo for sirukumab PFS provided for this study is supplied in a matching presentation.

However, as a contingency, sirukumab may also be supplied as a single-use prefilled syringe-Ultrasafe (PFS-U), which is a ready to use liquid filled 1-mL-long syringe product supplied with a passive safety needle guard (UltraSafe Passive Delivery System, Safety Syringes, Inc.) for SC administration. Placebo for sirukumab PFS-U will also be supplied as appropriate.

The needle shield on the PFS (either assembled into UltraSafe needle guard or autoinjector/prefilled pen) is made with a derivative of natural rubber latex, which may cause allergic reactions in individuals sensitive to latex.

Prednisone for the pre-specified standard blinded taper will be provided by the Sponsor. The prednisone used in the blinded taper of this study is manufactured by Jubilant Cadista (Salisbury, MD) and supplied to the Sponsor by Myoderm (Norristown, PA).

Prednisone for the unblinded (open-label) taper will be provided by the sites or by the Sponsor in certain countries in order to comply with local regulations. Use of standard release prednisone is required for the open-label taper. Prednisone doses between 60 and 20 mg will be administered during the unblinded (open label) taper. Subjects who reach 20 mg will receive the blinded prednisone from that visit. Prednisone doses below 20 mg and/or matching placebo will be provided in blister packs for blinded administration. Subjects should take their prednisone daily dose in one single daily administration in the morning.

	Study Treatment		
Product name:	Sirukumab	Placebo	Prednisone/ prednisone placebo
Dosage form:	1.0 mL Pre-filled syringe	1.0 mL Pre-filled syringe	Tablets
Unit dose strength(s)/Dosage level(s):	100 mg/mL or 50 mg/mL	--	Up to-60 mg/day
Route of Administration	SC	SC	Oral
Dosing instructions:	SC q2w (treatment arms A & B) SC q4w (treatment arm C)	SC q2w (treatment arms D & E)	20-60 mg/day open-label then 0-18 mg/day taper (blinded)

Note subjects randomized to treatment arm C will alternate between sirukumab 50 mg SC and matching placebo SC injections in order to maintain the blind (see Section 6.4).

Instructions for use of the SmartJect autoinjector will be provided to subjects and to the sites. Each step in the instructions is essential to ensure a successful delivery of study drug. It is important that the autoinjector is held against the skin at the injection site with sufficient force to disengage the safety interlock and make the push button actuatable, the actuation button is pressed to begin the injection cycle, and the autoinjector remains in place until the complete dose is delivered (second audible click or 15 seconds).

The investigator and designated site staff will be trained in the use of the SmartJect autoinjector for the SC administration of study drug. The trained site staff will be responsible for training each individual subject in the proper use of the SmartJect autoinjector. The study drug will be administered by the trained site staff during site visits until the subject is trained and confident in the use of the SmartJect auto-injector to self-administer study drug at home. If necessary a family member or carer will be trained in the use of the SmartJect autoinjector in order to administer the injection to the subject.

Study drug will be administered by the trained site staff at the Baseline and Week 2 visits. At the Week 4 visit, subjects will self-administer study drug at the site under the supervision of the trained site staff unless they are unable or unwilling to do so. In this case, study drug will be administered by the trained site staff.

At the relevant site visits, study drug must be withheld until all patient reported outcomes (PROs) questionnaires have been completed and blood samples taken for pharmacokinetic (PK) analysis of sirukumab serum concentrations (in order to collect a pre-dose sample). The visits scheduled for PRO and PK analyses are provided in Section 7.1, Time and Events Tables.

Once these assessments are completed, subjects will self-administer study drug at the site or may have study drug administered by the trained site staff. Subjects will self-administer study drug at home in between site visits. Subjects unable or unwilling to self-administer study drug at home may be able to attend the clinic between scheduled visits for study drug administration.

Subjects who self-administer study drug at home, should be instructed to take the study drug q2w but no more than  $\pm 4$  days from the scheduled dosing day. Administrations of study drug must be at least 7 days apart. Subjects will be instructed to contact the investigator promptly in the event of any signs of an allergic reaction, infection or bleeding.

